## 3. EXPERIMENTAL PLAN

### 3.1 Study Design

This is a first-in-human (FIH), multicenter, non-randomized, open-label, phase 1 study evaluating AMG 397 administered orally in adult subjects with selected RR hematological malignancies.

This study will consist of dose escalation (Part 1) to evaluate safety and tolerability and estimate the MTD/RP2D of AMG 397 using a Bayesian Logistic Regression Model (BLRM) in the following groups:

- Group 1A will consist of subjects with RR MM and/or NHL
- Group 1B will consist of subjects with RR AML

This will be followed by a dose expansion (Part 2) to gain further efficacy and safety experience with AMG 397 in adult subjects with RR MM, DLBCL, and AML.

#### **Dose Escalation– Part 1**

During dose escalation (Part 1), AMG 397 will be administered orally once daily for 2 consecutive days followed by 5 days break at a weekly interval, as part of a 28-day treatment cycle.

Dose escalation will estimate MTDs for Group 1A and Group 1B using an adaptive, BLRM design. [Table 3](#) shows the planned dose levels for dose escalation. The Dose Level Review Team (DLRT) will review data, monitor safety, and make decisions on any dose escalation/change. For more details regarding the dose escalation, please see [Section 6.2.1.2](#)

**Table 3. Planned Doses per Dose Cohort Level**

Dose Cohort Levels	Dose (mg) PO
1	80
2	160
3	320
4	640

Dose escalation for Group 1A and Group 1B will begin with 2-4 subjects treated at the lowest planned dose level of 80 mg. Dose escalation will follow the planned schedule described above with 2-4 subjects treated in each cohort.

DLRT will convene to review the safety data and determine the appropriate dose to be implemented. Dose escalation/de-escalation decisions will be guided by the BLRM model of dose toxicity. Skipping of planned dose levels is not allowed. Dose escalation decisions will not be made until all subjects in a cohort(s) are monitored through the DLT-observation period of 28 days following treatment initiation. Intermediate dose levels and alternative dosing schedule(s) may be explored based on emerging pharmacokinetic and safety data per the decision of the DLRT.

Dose escalation for both Group 1A and 1B respectively, will continue until any of the following events:

- The highest planned dose level for each group is determined to be safe and tolerable (minimum of 6 evaluable subjects)
- MTDs are identified for each group where BLRM repeats the recommendation of a dose level (minimum of 6 evaluable subjects)
- The maximum of 30 evaluable subjects have been enrolled in each group. If fewer than 6 subjects are treated at the MTD/RP2D, additional subjects may be enrolled to confirm safety and tolerability.

Intermediate doses and alternative dosing schedule(s) may be explored based on emerging pharmacokinetic and safety data as decided by the DLRT.

### **Lead-in Dosing**

Due to the potential risk of TLS for subjects affected by hematologic malignancies, it is anticipated that lead-in dosing may be implemented. At any point during the study, when an event meeting clinical or laboratory TLS per Cairo-Bishop criteria ([Appendix K](#) and [Appendix L](#)) is observed within seven days after therapy with AMG 397, lead-in dosing may be initiated to evaluate a step-wise dose escalation for all subsequent dosing. See [Figure 2](#) for an example of lead-in dosing. See [Section 6.2.1.1.1](#) for more details

### **Dose Expansion – Part 2**

Upon completing the dose escalation part of the study and depending on data obtained, dose expansion may proceed in groups with selected RR hematological malignancies below:

- Group 2A will consist of subjects with Multiple Myeloma (MM)
- Group 2B will consist of NHL subjects with Diffuse Large B-cell Lymphoma (DLBCL)
- Group 2C will consist of subjects with Acute Myeloid Leukemia (AML)

Dose expansion in all of these groups may take place concurrently. The maximum tolerated dose (MTD) for each indication, identified from the dose escalation phase, will inform the dose expansion phase.

### **Intra-subject Dose Escalation**

Subjects who complete the DLT period may proceed to a higher dose level for the following treatment cycle once the next dose cohort has been deemed safe by the DLRT and after consultation with the PI and sponsor as long as no DLT has been reported for this subject during or after completion of the DLT period.

The overall study design is described by a [study schema](#) at the end of the protocol synopsis section.

The study endpoints are defined in [Section 10.1](#).

### **3.2 Number of Sites**

This study will be conducted at up to 20 sites globally in Australia, Europe, Japan and the United States. Additional regions, countries, or sites may be added.

Sites that do not enroll subjects into an open cohort within 4 months of site initiation during dose escalation or expansion may be closed or replaced.

### **3.3 Number of Subjects**

Participants in this clinical investigation shall be referred to as “subjects”.

Up to 90 evaluable subjects will be enrolled in the study. Up to 60 evaluable subjects will be enrolled during dose escalation (up to 30 in both Groups 1A and 1B). Up to 30 evaluable subjects will be enrolled into the dose expansion part (up to 10 each for Groups 2A, 2B, and 2C). Based on emerging data, additional subjects may be enrolled.

The rationale for the number of subjects required is detailed in [Section 10.3](#).

### **3.4 Replacement of Subjects**

During dose escalation, subject(s) may be replaced if:

- Subject(s) is not DLT-evaluable. See [Section 6.2.1.2](#) for definition of DLT-evaluable
- Subject(s) discontinues treatment for any reason other than a DLT during the DLT-observation period

Additional subjects may also be enrolled if Amgen’s medical monitor determines that the minimum required number(s) of evaluable subjects have not been enrolled in each cohort.

### 3.5 Estimated Study Duration

#### 3.5.1 Study Duration for Subjects

The study duration for each subject is approximately 8 months consisting of up to 21 days in the screening period, approximately 6 months of treatment period, an EOT visit, and a SFU visit approximately 28 (+ 7) days after their last dose of AMG 397.

For dose expansion part only, long-term follow up (LTFU) will be conducted every 3 months from the last visit for up to 1 year from the first dose of AMG 397, for all subjects who have not withdrawn consent to assess for survival and/or the commencement of subsequent cancer therapy.

This study duration may vary depending on the subject's disease, ability to tolerate AMG 397 and/or willingness to participate in the study.

**End of study (EOS) for an individual subject:** The date when the subject completes the final protocol-specified procedure or SFU/LTFU visit whichever is later. This date will be recorded on the EOS electronic CRF (eCRF)

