**Table 4. Schedule of Assessments**

CYCLE(S)	SCREENING	TREATMENT																								EOT	SAFETY FOLLOW-UP	LTFU (26)					
		1												2					3			Every cycle from 3 & beyond											
		1												2					3	1	2	3	1										
WEEK(S)	DAY(S)	-21	-1	1								2								3	4	8					15	22	1	8	15	1	
DAY(S)	Pre-dose	0	1	2	3	5	8	12	Pre-dose	0	1	2	3	5	8	12	24h after D2 dose	48h after D2 dose	Pre	0	2	3	5	Pre-dose unless specified									
HR(S) (relative to time of dosing)																																	
Survival/Subsequent anti-cancer therapy (6)																																	
LAB ASSESSMENTS																																	
AMG 397 PK (7)		X		X	X	X	X	X	X	X	X	X	X	X	X	X	X	X	X	X	X	X	X	X	X	X	X	X	X				
CBC with diff (8)	X	X	X						X							X	X	X						X	X	X	X	X	X				
Chemistry (9)	X	X	X			X		X	X	X			X		X	X	X	X						X	X	X	X	X	X				
Coagulation	X	X	X						X						X	X	X						X	X	X	X	X	X	X				
Pregnancy test (10)	X	X																								X		X	X				
Urine sample collection (11)	X	X					X	X						X					X				X				X		X				
Hepatitis serology, HIV	X																																

Footnotes are defined at the end of [Table 5](#)

Approved

Table 4. Schedule of Assessments

CYCLE(S)	SCREENING	TREATMENT																		EOT	SAFETY FOLLOW-UP	LTFU (26)																
		1												2			Every cycle from 3 & beyond																					
WEEK(S)		1												2			3		1	2	3	1																
DAY(S)	-21 to -2	-1	1						2						3	4	8			15	22	1	8	15	1													
HOURL(S) (relative to time of dosing)			Pre-dose	0	1	2	3	5	8	12	Pre-dose	0	1	2	3	5	8	12	24h after D2 dose	48h after D2 dose	Pre	0	2	3	5	Pre-dose unless specified												
BIOMARKER and DISEASE ASSESSMENTS																																						
Bone marrow aspirate (12)	X																																					
Whole blood Na/Hep (13)		X				X	X				X																											
Whole blood Cytochex (14)		X									X								X	X	X																	
Plasma	X																																					
Serum	X																																					
Cell Pellet	X																																					
MM SUBJECTS ONLY																																						
SPEP/UPEP/Immunofixation (15)	X																																		X		X	X
SFLC (16)	X																																		X		X	X
Beta-2 microglobulin	X																																					X
Quantitative Ig (17)	X																																					X

Approved

Footnotes are defined at the end of [Table 5](#)

Table 4. Schedule of Assessments

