#### **7.4.5 Long-term Follow-up (Dose expansion subjects only)**

Long-term follow up (LTFU) will be conducted every 3 months from the last visit for up to 1 year from the first dose of AMG 397 for all subjects who have not withdrawn consent by telephone or chart review to assess for survival, disease progression and/or the commencement of subsequent cancer therapy only.

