## **10.6.3 Secondary Endpoints**

### **10.6.3.1 Efficacy Endpoint Analyses**

The analyses on PFS and OS will be done only using data from dose expansion subjects; other efficacy endpoints will be analyzed using data from both dose escalation and dose expansion.

The number and percentage of subjects by overall response and overall response category will be calculated and tabulated. Using the Kaplan Meier estimate, the PFS at 6 and 12 months and the OS at 6 and 12 months with corresponding 90% CI will be tabulated. Listings will be produced for all subjects indicating the OS, PFS, time to

Approved

response and duration of response. Kaplan Meier curve will be presented for OS, PFS, time to response and duration of response with estimates for rates and 80% CI at selected weeks.

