- **IMWG-URC for MM**
- **2017 ELN criteria for AML**
- **Revised IWG for MDS**
- **Lugano Classification for NHL**

Dose Limiting Toxicity (DLT)

Unless otherwise specified, investigators determine whether an adverse event qualifies as a DLT per the definition described in the protocol.

DLT Observation Period

The DLT observation period is defined as, at minimum, 28 days after the initial dose of AMG 397. If lead-in dosing period is initiated, the DLT-observation period is defined as the amount of time for subject(s) for each dose cohort to receive at least 1 week of lead-in dose and 3 weeks of target dose.

Duration of Response (DOR)

Duration of response is calculated for subjects who have achieved response (PR or better). It is defined as time from the first observation indicating a response to the subsequent date of disease progression or death, whichever is earlier.

DOR time in months: (date of disease progression or death - date of the first observation of response +1)/30.4

Subjects without disease progression or death until the analysis data cut-off date will be censored at the last adequate disease assessment date.

Fridericia-corrected QT Interval (QTcF)

The Fridericia correction will be calculated from the investigator reported QT (msec) and RR interval (msec): $QTcF = QT / (RR/1000)^{1/3}$

Investigational Product (IP)

IP is used in reference to AMG 397.

Overall Response Rate (ORR)

ORR is the incidence of either PR or better based on investigator assessment. All subjects that do not meet the criteria for response (PR or better) by the analysis cutoff date will be considered as non-responders.

Progression-free survival (PFS)

PFS time is calculated as time from first dose of IP date to disease progression date or death due to any cause, whichever is earlier.

PFS time in months: (date of disease progression or death - first dose of IP date +1)/30.4

Subjects without disease progression or death until the analysis data cut-off date will be censored at the last adequate disease assessment date. If no post-baseline disease assessment, censoring is at the first dose of IP date.

Overall survival (OS)

OS is defined as the time from first dose of IP date until death due to any cause.

OS time in months: (date of death - first dose of IP date +1)/30.4

Patients without event will be censored at their last date known to be alive.

Study Day

Post study day 1: study day = (date –Study Day 1) + 1

Pre study day 1: study day = (date –Study Day 1)

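### The Protocol contradicts itself on whether progression is collected in long-term follow-up, and under the narrower reading the SAP's PFS and DOR rules make follow-up length depend on whether the subject dies

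*Protocol*

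**What the plan says.** **LTFU content (Protocol).**
- Section 3.5.1, and the synopsis under Procedures, set the purpose as "to assess for survival and/or the commencement of subsequent cancer therapy". Progression is not listed.
- The Table 4 row label begins "Survival/Subsequent anti-cancer therapy (6" (the 6 points to footnote 6). Progression is not listed there either.
- Section 7.4.5 and footnote 26 to Tables 4 and 5 have contacts by telephone or chart review "to assess for survival, disease progression and/or the commencement of subsequent cancer therapy only". The Table 4 LTFU column heading cites footnote 26.
- Contacts take place "every 3 months from the last visit for up to 1 year from the first dose of AMG 397", in dose expansion subjects only.

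**Disease assessments (Protocol).** Footnotes 23 and 25 schedule NHL imaging and AML marrow at Cycle 2, every 8 weeks thereafter, and at EOT. Nothing is scheduled after EOT in any disease.

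**Event and censoring rules (SAP Section 5).** A PFS event is "disease progression date or death due to any cause, whichever is earlier". There is no limit for missed assessments or for new therapy. Otherwise: "Subjects without disease progression or death until the analysis data cut-off date will be censored at the last adequate disease assessment date". DOR follows the same pattern. The SAP does not say what makes an assessment adequate.

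**Planned outputs.** Protocol Section 10.6.3.1 states "The analyses on PFS and OS will be done only using data from dose expansion subjects" and plans that "the PFS at 6 and 12 months and the OS at 6 and 12 months with corresponding 90% CI will be tabulated". SAP Section 9.5 plans Kaplan-Meier estimates, names no 6-month landmark, and may drop a time-to-event summary with fewer than 10 events.

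**The concern.** The two versions of the LTFU text give different data. Suppose a subject stops for toxicity at month 2 without progression, progresses at month 4 and dies at month 8. Under Section 7.4.5 the progression is picked up at the first LTFU contact, about month 5 or 6 (3 months after a last visit at month 2 or 3). Under Section 3.5.1 it is never asked about, and the subject counts as progression-free until death at month 8. A second subject who stops at month 2 and stays alive is censored at about month 2.

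Among subjects who stop without progression, the length of PFS follow-up then depends on the outcome. Those who die are kept at risk until death, and those who survive leave at EOT. Kaplan-Meier assumes that censoring is unrelated to outcome, and here it is not.

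At stake are PFS and DOR, both secondary efficacy endpoints, and the planned 6- and 12-month PFS in the expansion groups. Progression that is not asked about at a contact may not be recoverable later.

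**Working it through.** The documents give no PFS rate, so there is no planned figure to reproduce. The question is how far 6-month PFS moves between the two LTFU texts.

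**Inputs from the documents.** Assessments at weeks 4, 12, 20, 28 and so on, plus EOT; LTFU contacts every 3 months to 12 months from first dose; SAP Section 5 event and censoring rules; 10 subjects per expansion group (Protocol Section 3.3).

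**Assumptions, none from the documents.** Median time to progression 2, 4 or 6 months. Death before progression at 0.2 times the progression hazard. Median survival after progression 3, 6 or 12 months. Probability of stopping for reasons other than progression by month 6 of 0, 15, 30 or 50%, before allowing for competing events; at 30% the share who actually stop first is about 12 to 21%. After stopping, progression hazard ×1 to ×3 and death hazard ×1 or ×3.

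**Method.** 200,000 simulated subjects per scenario, Kaplan-Meier at 6 months, three follow-up rules:
- (a) reference: the 8-week schedule continues after treatment stops;
- (b) survival only after EOT (synopsis and Section 3.5.1);
- (c) progression collected every 3 months (Section 7.4.5 and footnote 26).

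The error is the 6-month PFS under (b) or (c) minus that under (a). Selected results in percent, with 12-month follow-up, death hazard unchanged after stopping and one fixed setting of survival after progression (differences were taken before rounding):

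| Stopping | Median progression (months) | Progression hazard after stopping | (a) | (b) | (b)−(a) | (c)−(a) |
|---|---|---|---|---|---|---|
| 15% | 4 | ×1 | 36.3 | 36.2 | −0.1 | +0.1 |
| 30% | 4 | ×1 | 36.1 | 35.8 | −0.3 | +0.3 |
| 30% | 4 | ×2 | 33.4 | 35.8 | +2.4 | +0.6 |
| 50% | 4 | ×3 | 28.2 | 35.3 | +7.1 | +1.3 |
| 50% | 6 | ×1 | 50.7 | 48.8 | −1.9 | +0.5 |

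Over the whole assumed range, (b)−(a) runs from −2.5 to +7.1 points and (c)−(a) from 0.0 to +1.3. With nobody stopping before progression, (b)−(a) is 0.

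**Why the sign varies.** Unseen progressions push PFS up. Deaths that count after comparable survivors have been censored push it down. With hazards unchanged after stopping, the two roughly cancel or the second prevails. If progression speeds up off drug, the first prevails.

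**At the primary analysis** (6 months after the last subject, accrual over 3 to 12 months, 30% stopping, hazards unchanged), (b)−(a) is −3.1 to +0.5.

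**Scale.** In a group of 10, one subject is 1/10 = 10 points, and the simulated SD of the 6-month estimate is about 10 to 16 points. The SAP's expansion groups of 20 would reduce this by √2, to about 7 to 11.

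**The case against.** The best reply is that the operative text does collect progression. The Table 4 LTFU column points to footnote 26, footnote 26 names progression, and Section 7.4.5 agrees. The synopsis itself refers to the schedule of assessments for the full list of procedures. A reader might infer that a site working from Table 4 would record no progression. That is not supported: only the short row label omits it. What stands is that Section 3.5.1 and the synopsis say something different, and nothing in the Protocol says which text prevails.

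Section 8.1 also asks investigators to discuss continued assessments and endpoint collection with subjects who decline further product. This softens the gap but schedules nothing.

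A reader might also infer a definite upward bias in 6-month PFS of several points. Four scenarios with median progression of 3 or 4 months, 30 to 47% stopping first and continuous detection of progression do give errors of +8.6, +4.7, +4.8 and +2.5 under survival-only follow-up. Those figures include ordinary detection delay, which affects PFS under any LTFU text. Against the 8-week schedule continued off treatment, the same four scenarios give +3.0, +1.3, +0.1 and −0.5. The documents give no rate of stopping without progression, so no single figure can be defended.

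Nor do the documents support a reversed bias once progression is collected. That needs censoring at the last scan, with LTFU status never counting as an assessment. The SAP's wording is not limited to scans and leaves the point open.

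Finally, PFS is descriptive, no hypothesis is tested, and sampling error in these groups exceeds the possible bias. That limits the consequence but does not remove the contradiction.

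**Conclusion.** The contradiction is real and lies within one document, so it does not depend on which SAP version applies. The route to bias also holds: deaths count without a limit, event-free subjects are censored at the last adequate assessment, and LTFU is the only planned source of later progression data.

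The possible bias in expansion-phase PFS and DOR is conditional. It needs the narrower LTFU text to be followed and a meaningful share of subjects to stop without progression. Subjects who stop because of progression are unaffected. For 6-month PFS the error is about −2.5 to +7.1 points under assumed rates, and at most about 1.3 points in these scenarios if progression is collected every 3 months. The effect on DOR was not quantified.

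One limit applies to the analysis side. The LTFU text and the 6-month landmark come from the Amendment 1 Protocol, while the event and censoring rules come from a SAP written for Amendment 4, which was not supplied and covers a redesigned study. The point is worth correcting because the correction is almost free, not because a large bias has been shown.

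**What to change.** 1. **Protocol.** Align the synopsis, Section 3.5.1 and the Table 4 row label with Section 7.4.5 and footnote 26, so that each existing LTFU contact records progression (yes/no, with date) and the start date of any new cancer therapy. If Amendment 4 already does this, only the SAP items remain.
2. **SAP Section 5.** State whether a progression status obtained at an LTFU contact counts as an adequate disease assessment for censoring. Moving the censoring date to the last contact is one convention among several and is not required here; the SAP should choose and say so.
3. **SAP Section 9.5.** Add a sensitivity analysis of PFS and DOR that applies the same follow-up cut-off to events and non-events, for example both cut at EOT.

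The cost is three wording changes, an added field on an existing telephone or chart-review form, and short SAP text. No visits or scans are added. The downside is that progression learned by telephone or chart review is dated less exactly than progression found at a scheduled assessment.

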#### 3.5.2 End of Study

**Primary Completion:** The primary completion date is defined as the date when the last subject is assessed or receives an intervention for the final collection of data for the primary endpoint(s), for the purposes of conducting the primary analysis, whether the study concluded as planned in the protocol or was terminated early.

If the study concludes prior to the primary completion date originally planned in the protocol (ie, early termination of the study), then the primary completion will be the date when the last subject is assessed or receives an intervention for evaluation in the study (ie, last subject last visit).

**End of Study:** The end of study date is defined as the date when the last subject is assessed or receives an intervention for evaluation in the study (ie, last subject last visit), following any additional parts in the study (eg, long-term follow-up), as applicable.

## 4. SUBJECT ELIGIBILITY

### 4.1 Inclusion Criteria

101. Subject has provided informed consent prior to initiation of any study-specific activities/procedures.
102. Age  $\geq$  18 years old

103. Pathologically-documented, definitively-diagnosed relapsed or refractory MM, NHL, or AML ([Appendix G](#)) and is intolerant to, or considered ineligible for available therapies known to provide clinical benefit.
- 104. MM subjects only:**
- Measurable disease per the IMWG response criteria ([Appendix E](#); assessed within 21 days prior to enrollment), as indicated by one or more of the following:
    - Serum M-protein  $\geq 0.5$  g/dL
    - Urine M-protein  $\geq 200$  mg/24 hours
    - For Subjects who do not meet 1 of the 2 prior criteria:
      - Serum Free Light Chain (sFLC)  $\geq 10$  mg/dL ( $\geq 100$  mg/L) **AND** an abnormal sFLC ratio ( $< 0.26$  or  $> 1.65$ ) as per the IMWG response criteria
- 105. NHL subjects only:**
- Radiographically measurable disease with a clearly demarcated nodal lesion at least 1.5 cm in its largest dimension or a target extranodal lesion at least 1.0 cm in its largest dimension
- 106. AML subjects only:**
- Pathologically confirmed diagnosis of AML as defined by the WHO Classification ([Appendix H](#))
  - More than 5% blasts in bone marrow
- 107. MM and NHL subjects only:**
- Hematological function, as follows without transfusion or growth factor support within 2 weeks prior to study day 1:
    - Absolute neutrophil count  $\geq 1.0 \times 10^9/L$
    - Hemoglobin  $> 8$  g/dL
    - Platelet count  $\geq 75 \times 10^9/L$

**NOTE for MM subjects only:** Platelet count  $\geq 50 \times 10^9/L$  (in subjects where  $< 50\%$  of bone marrow nucleated cells were plasma cells) OR  $\geq 30 \times 10^9/L$  (in subjects where  $\geq 50\%$  of bone marrow nucleated cells were plasma cells) without transfusion or growth factor support are allowed into the study.
108. Eastern Cooperative Oncology Group (ECOG) performance status of  $\leq 2$  ([Appendix F](#))
109. Life expectancy of  $> 3$  months, based on the opinion of the investigator
110. Able to swallow and retain orally administered medication and does not have any clinically significant gastrointestinal abnormalities that may alter absorption

Approved

111. Hepatic function, as follows:

- Aspartate aminotransferase (AST) and alanine aminotransferase (ALT) < 3 x upper limit of normal (ULN)
- Total bilirubin (TBIL) < 1.5 X ULN (except subjects with Gilbert's syndrome)

112. Cardiac function, as follows:

- Cardiac ejection fraction  $\geq$  50% and no evidence of pericardial effusion as determined by an ECHO or MUGA
- No clinically significant ECG findings.

113. Renal function as follows:

- Calculated or measured creatinine clearance (CrCl) of  $\geq$  30 mL/minute calculated using the formula of Cockcroft and Gault  $[(140 - \text{Age}) \times \text{Mass (kg)} / (72 \times \text{serum creatinine mg/dL})]$ . Multiply result by 0.85 if female.

